# 3.7 Interim analysis

An interim analysis may be conducted by the Sponsor's decision after receipt of efficacy data for Angal and ANTI-ANGIN® FORMULA after 3 days of therapy, on Day 4, for at least 100 patients in every arm. The interim analysis includes demographic data, data of anamnesis and concomitant therapy, available data on efficacy and safety of Angal and ANTI-ANGIN® FORMULA drugs.

Safety will be evaluated for all the patients who received at least one dose of the study drug as at the interim analysis date. Based on the interim analysis results, the main and additional statistical parameters of efficacy and safety of the study drug, ZAO Sandoz shall be entitled to decide to discontinue the trial prematurely.

No significance level correction for the interim statistical analysis is envisaged.

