#### 4.6 Description of rules for termination of the trial parts or the trial as a whole

The trial may be terminated on the following grounds:

- 1. Upon the Sponsor's initiative: availability of new toxicological or pharmacological data, or data on SAE which require re-consideration of the previous evaluation of the benefit/risk ratio.
- 2. Upon the Sponsor's initiative: AEs incidence or severity require the trial termination.
- 3. Upon the Sponsor's initiative: other reasons including administrative ones.
- 4. Upon the decision of the regulatory authorities.

The trial may be terminated at a specific trial site in case the patients enrollment or data quality are unsatisfactory, or it is reasonable to assume a breach of GCP and/or Declaration of Helsinki, or other serious protocol deviations.

In case of early termination of the trial, the Sponsor must inform the trial site personnel as well as regulatory authorities with indication of the reason thereof. The rules for trial termination for every participant are described in Section 5.3.

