### 9.3 Applicable significance level

All statistical analyses in this trial will be conducted at 95% significance level (a threshold p value for confirmation of statistical significance is below 0.05), except for the primary endpoint where an one-sided statistical criterion will be used with 97.5% significance level (a threshold p value is below 0.025). The two-sided statistical criteria will be used for all other parameters.

For the primary endpoint evaluation, 90% CI will be calculated for the proportions difference with further evaluation of its lower boundary limit.

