## 9.8. Interim analysis

An interim analysis may be conducted by the Sponsor's decision after receipt of efficacy data for Angal and ANTI-ANGIN® FORMULA after 3 days of therapy, on Day 4, for at least 100 patients in every arm. The interim analysis includes demographic data, data of anamnesis and concomitant therapy, available data on efficacy and safety of Angal and ANTI-ANGIN® FORMULA drugs.

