## 3.10 Significance level

All statistical analyses in this trial will be conducted at 95% significance level (a threshold p value for confirmation of statistical significance is below 0.05), except for the primary endpoint where a one-sided statistical criterion will be used with 95% significance level (a threshold p value is below 0.05). The two-sided statistical criteria will be used for all other parameters.

For the primary endpoint evaluation, 90% CI will be calculated for the proportions difference with further evaluation of its lower boundary limit.

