## 4 Analysis plan

For non-inferiority confirmation, a two-sided 90% CI will be calculated for the proportion difference of the primary efficacy parameters (no pain after 3 days of therapy on Day 4 according to TSS) with further evaluation of its lower boundary limit.

A non-inferiority conclusion will be made relating to the primary parameter only which will confirm the claimed efficacy. Secondary variables (including secondary efficacy and safety parameters) will be used for the research interest. Correction for multiple comparisons is not envisaged due to the trial arms number.

Descriptive statistics will include data for all randomized patients. Descriptive statistics parameters to be calculated for the quantitative variables are listed below:

- Quantity of observations (n);
- Arithmetic mean (M);
- Standard deviation (SD);
- 95% confidence interval for the mean (95% CI);
- Minimal value (min.);
- Maximal value (max.);
- Median (Me);
- Interquartile range (IQR).

For the variables presented as qualitative and serial parameters, the absolute (n) and relative (%) incidences will be calculated for every category, as well as 95% CI (unless otherwise specified).

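### The optional interim efficacy look has no boundary and no alpha correction, so type I error is not controlled if non-inferiority can be claimed there

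*SAP*

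**What the plan says.** SAP 3.7 and Protocol 9.8 both allow an interim analysis at the sponsor's discretion, "on Day 4, for at least 100 patients in every arm", covering efficacy and safety by drug. The protocol synopsis has a similar entry at 100 per arm. The trial is open (Protocol 4.3.2).

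Only SAP 3.7 says what may follow. On the interim efficacy and safety parameters, "ZAO Sandoz shall be entitled to decide to discontinue the trial prematurely". It then says: "No significance level correction for the interim statistical analysis is envisaged".

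Other relevant passages:

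- Protocol 9.8 gives no stopping right and makes no statement on alpha.
- Protocol 9.4 refers termination to Protocol 4.6. That section does not name efficacy as a ground, but it lets the sponsor stop for "other reasons including administrative ones".
- SAP 4 says "Correction for multiple comparisons is not envisaged due to the trial arms number". That reason concerns the number of arms, not the number of looks.
- The primary one-sided level is 0.025 in Protocol 9.3 and 0.05 in SAP 3.10. Both sections, and the decision rule in SAP 4.1.2, use a two-sided 90% Newcombe interval.

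**The concern.** SAP 4 makes the primary endpoint the trial's only confirmatory conclusion. SAP 3.7 allows that endpoint to be examined by arm before the end, gives the sponsor a free decision to stop on what it sees, and waives any adjustment. Nothing says whether a favourable interim result could be reported as non-inferiority. If it could, the nominal level is spent twice, and the final report could not state the error rate of its main claim.

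The 0.025 versus 0.05 conflict is a separate matter. The problem here exists at either level.

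**Working it through.** **Inputs from the documents.** Margin 14.5 points; comparator rate 63% and study drug rate 65% under the planning assumptions; 1:1 allocation; 128 evaluable and 140 randomised per arm; interim at 100 or more per arm; Newcombe interval for the difference.

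**Assumptions.** The interim success rule is the same as the final rule. Non-inferiority is met when the lower Newcombe limit for p1 − p2 exceeds −14.5%, the reading that fits the stated hypotheses. Two limits are used: the 90% CI of the stated decision rule, and a 97.5% one-sided limit, which is my translation of the protocol's 0.025.

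**The plan's own figure.** The documents give no overall error for a two-look design. They give 128 per arm for 80% power at one-sided 0.025. Exact enumeration with the Newcombe limit gives 79.2% power at 128, close enough to use 128 as the final size.

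**Formula for the limit.** L = (p̂1 − p̂2) − √[(p̂1 − l1)² + (u2 − p̂2)²]. Here l1 and u2 are the Wilson limits [p̂ + z²/2n ∓ z√(p̂(1 − p̂)/n + z²/4n²)] / (1 + z²/n), with z = 1.645 (90% CI) or 1.960 (97.5% limit).

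**Null case.** The true difference lies on the margin: 63% − 14.5% = 48.5% versus 63%. All pairs of binomial counts at the interim are enumerated. Pairs that cross count as claims. The rest are carried forward with the counts from the remaining patients and tested at the final look.

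| Interim n per arm | Final n per arm | 97.5% one-sided limit | 90% CI |
|---|---|---|---|
| none | 128 | 2.81% | 4.91% |
| 100 | 128 | 3.99% | 7.37% |
| 110 | 128 | 3.57% | 6.87% |
| 120 | 128 | 3.30% | 6.06% |
| 125 | 128 | 3.16% | 5.71% |
| none | 140 | 2.77% | 4.87% |
| 100 | 140 | 4.13% | 7.65% |

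The increase from a look at 100 is:

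- final 128: 3.99 − 2.81 = 1.18 points and 7.37 − 4.91 = 2.46 points;
- final 140 (nobody lacking Day 4 data): 4.13 − 2.77 = 1.36 points and 7.65 − 4.87 = 2.78 points.

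**Sensitivity to the control rate.** With assumed control rates of 55% to 70% and looks at 100 and 128, the error is 3.8–4.0% and 7.3–7.5%.

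**Cross-check by normal theory.** Error = 1 − Φ₂(c, c; ρ), with ρ = √(100/128) = 0.884. For c = 1.960 this gives 3.59%; for c = 1.645, 6.95%.

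**How often the interim would decide.** Under 65% versus 63%, where non-inferiority is true, the chance of crossing at 100 per arm is 70% (97.5% limit) or 79% (90% CI). These are not false-positive rates. They show that an unadjusted interim look would often be the one that ends the trial.

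**The case against.** The strongest reply is that SAP 3.7 grants a right to discontinue, not to declare success. The synopsis requires at least 256 patients for the statistical analysis, Protocol 9.4 routes termination to a list with no efficacy ground, and SAP 1 says that no changes from the protocol are envisaged. Together these make an interim success claim the less natural reading. That stands as far as it goes, and it is why the conclusion is conditional. But none of these passages bars a claim, the list in 4.6 is open-ended, and SAP 3.7 expressly bases stopping on efficacy parameters.

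Three narrower points also stand:

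- The documents prescribe a 90% CI throughout, so the 97.5% results rest on an assumed rule.
- Part of the excess is not due to the second look. A single look at 100 per arm under the 90% CI rule already has 5.72% error because of discreteness, and normal theory puts the increase nearer 6.95 − 5.00 = 1.95 points.
- The look is optional, and the figures take the worst case, a true difference exactly on the margin.

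These points affect the size. They do not remove the defect: a confirmatory plan has to settle before unblinded data are seen what an interim result may be used for.

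**Conclusion.** The concern holds. If the look takes place and non-inferiority may be claimed from it, type I error exceeds both stated levels: about 7.4% under the 90% CI rule and about 4.0% under a 97.5% one-sided limit, for looks at 100 and 128 per arm. With a final 128, the look itself adds at most about 2.5 and 1.2 points respectively; with a final 140, about 2.8 and 1.4. Later looks add less. About 0.3 points of the excess over 0.025 comes from the Newcombe limit even with one look (2.81% against 2.50%).

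The result depends on the interim using the unadjusted final criterion. If stopping is confined to futility or safety, there is no inflation. Because the point bears on the only confirmatory claim and is simple to close, it should be fixed before any interim data are examined.

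**What to change.** Replace the last sentence of SAP 3.7, and add to Protocol 9.8:

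> *The interim analysis will not be used to stop for, or to claim, non-inferiority; the primary test is performed once, at the final analysis.*

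Align the synopsis interim entry with this. Stopping for safety is unaffected.

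If early stopping for success is wanted, write instead:

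> *Non-inferiority may be claimed at the interim only if the lower limit of the two-sided 99.8% Newcombe CI exceeds −14.5%.*

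With looks at 100 and 128 this leaves the error at the single-look values of 2.81% or 4.91%, and 28% of trials would cross at the interim under 65% versus 63%. Neither wording removes the small Newcombe excess over 0.025.

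A spending function is also possible. It must be stated as CI levels for the reconciled alpha and the actual information fraction, and then checked exactly. O'Brien-Fleming-type spending at 100/128 gives a 97.8% then a 95.7% CI at alpha 0.025, with exact error 2.5%. At alpha 0.05 it gives 94.7% then 91.5%, and the exact error is still 5.7%, so that version would need tightening.

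**Cost.** One sentence in the SAP and one in the protocol, plus the approvals that Protocol 11.2 requires for an amendment. The sample size does not change. The sponsor gives up early stopping for success, or accepts a stricter bar for it.

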# 3.8 Acceptable deadlines for visits and a scope of investigations

The data obtained at Visit 1 (Day 1) will be considered to be the initial data for the endpoint analysis.

# **3.8.1** Screening: Visit 1 (Therapy Day 1)

Visit 1 is scheduled for Day 1. At this visit, the doctor evaluates the patient's eligibility for the trial. If no non-inclusion criteria are met, the patient undergoes randomization, is given the study drug/comparator drug and a patient's diary, and is instructed on the patient's diary completion requirements.

Screening visit procedures:

- Signing of the Informed Consent Form;
- Demographic data (date of birth, sex, age);
- Measurement of weight and height;
- Anamnesis gathering;

- Records on the concomitant therapy;
- Evaluation of inclusion/non-inclusion criteria;
- Evaluation of the throat pain intensity according to VAS;
- Fill-in of TSS questionnaire by the Investigator;
- Physical examination (including oropharynx);
- Measurement of the main vital signs;
- Hematology;
- Biochemistry;
- Urine pregnancy test;
- 12-lead ECG;
- Evaluation of inclusion/non-inclusion criteria;
- Randomization;
- Training for administration and handling of the study drugs;
- Dispensing of the study drugs;
- Provision with the patient's diaries and training on the fill-in rules;
- Initiation of therapy with the study drugs;
- Evaluation of adverse events (including based on results of the throat and pharynx examination).

## 3.8.2 Efficacy evaluation visit (Visit 2, Day 4 since the therapy initiation)

Visit 2 is conducted on Day 4; the patient must visit the trial site in the fasted state and bring the filled-in diary and unused drug. If Group B patients (ANTI-ANGIN® FORMULA) did not meet recovery criteria (total TSS  $\leq$  2) at Visit 2 (Day 4), they will require continuation of the therapy, and some procedures for those patients will be transferred for the next day (Visit 3, Day 5), see below. The patients will keep their diaries and the unused drugs.

#### Visit 2 procedures for the both groups:

- Collection of complaints, actualization of anamnesis;
- Records on the concomitant therapy;
- Physical examination (including oropharynx);
- Measurement of the main vital signs;
- Evaluation of adverse events (including based on results of the throat and pharynx examination);
- Evaluation of exclusion criteria;

- Compliance evaluation (diary completion, administration of the study drugs).

# Visit 2 procedures for patients from Group A (Angal) and Group B (ANTI-ANGIN® FORMULA) who achieved recovery criteria (total TSS ≤ 2):

- Hematology;
- Biochemistry;
- 12-lead ECG;
- Global evaluation of treatment tolerability during the trial by the physician and the patient;
- Return of the unused study drug;
- Return of the patient's diary.

# 3.8.3 Trial completion visit for Group B patients (Visit 3, Day 5)

This visit is for Group B patients only (ANTI-ANGIN® FORMULA) who did not achieve the recovery criteria (total TSS  $\leq$  2) at Visit 2 (Day 4).

Visit 3 is conducted on Day 5; the patient must visit the trial site in the fasted state and bring the filled-in diary and unused drug.

## Visit 3 procedures:

- Collection of complaints, actualization of anamnesis;
- Records on the concomitant therapy;
- Physical examination (including oropharynx);
- Measurement of the main vital signs;
- Evaluation of adverse events (including based on results of the throat and pharynx examination);
- Evaluation of exclusion criteria;
- Return of the unused study drug;
- Return of the patient's diary;
- Compliance evaluation (diary completion, administration of the study drugs).
- Hematology;
- Biochemistry;
- 12-lead ECG;

- Global evaluation of treatment tolerability during the trial by the physician and the patient.

# 3.8.4 Visit 4 (a follow-up, Day 6/7 from the therapy initiation)

A follow-up visit shall be conducted by phone to find out about the patient's state and any AEs. A visit 2 days after the therapy completion visit (e.g., on Day 6 or 7, depending on the arm and therapy duration).

Follow-up visit procedures (by phone):

- Evaluation of adverse events (without the throat and pharynx examination). In case of adverse events, the patient might be invited to visit the trial site.

#### 3.8.5 Unscheduled visits

The unscheduled visits will be conducted when necessary, e.g., in case of the index disease deterioration, AEs, or the study drug (Angal or ANTI-ANGIN® FORMULA) intolerability.

Every unscheduled visit, irrespective of its cause, must include the procedures listed below with completion of the relevant eCRF pages (Unscheduled Visit):

- Physical examination (including topical examination);
- TSS evaluation;
- Measurement of the main vital signs (blood pressure, heart rate, breathing rate, body temperature);
- 12-lead ECG (if it has not been done for the last 12 hours);
- Evaluation of adverse events;
- Evaluation of the concomitant therapy.

Other diagnostic and treatment procedures may be conducted depending on clinical situation and upon the Investigator's decision.

Taking into account frequency of visits, unscheduled visits may be conducted on the same days as scheduled ones but in a different time (e.g., in case of worsening the patient may visit the center in afternoon). All procedures for the planned visits are identical for the both arms at every trial stage, except for the Group B patients who, if the recovery criteria (total TSS  $\leq$  2) are not met at Visit 2 (Day 4), should continue the trial therapy and visit the trial site for scheduled Visit 3 Day 5).

## 3.8.6 Visit of premature discontinuation of the trial

Visit 2 procedures will be applied for the visit of premature discontinuation.

## 3.9 Null and alternative trial hypotheses

Based on the trial objectives, the following hypotheses were drawn for testing:

Null hypothesis (H0): Difference in the primary endpoint achievement incidence while using Angal, the study drug, and ANTI-ANGIN® FORMULA, the original drug, for treatment of acute infectious and inflammatory pharyngeal diseases will exceed 14.5% in favor of ANTI-ANGIN® FORMULA:

$$H_0: p_1 - p_2 \le -0.145$$

Alternative hypothesis ( $H_A$ ): Difference in the primary endpoint achievement incidence while using Angal, the study drug, and ANTI-ANGIN® FORMULA, the original drug, for treatment of acute infectious and inflammatory pharyngeal diseases will not exceed 14.5% in favor of ANTI-ANGIN® FORMULA:

$$H_A: P_1 - P_2 > -0.145$$

Where p1 and p2 is the primary endpoint achievement incidence while using Angal, the study drug, and ANTI-ANGIN® FORMULA, the original drug, respectively.

## 3.10 Significance level

All statistical analyses in this trial will be conducted at 95% significance level (a threshold p value for confirmation of statistical significance is below 0.05), except for the primary endpoint where a one-sided statistical criterion will be used with 95% significance level (a threshold p value is below 0.05). The two-sided statistical criteria will be used for all other parameters.

For the primary endpoint evaluation, 90% CI will be calculated for the proportions difference with further evaluation of its lower boundary limit.

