# Confidence Intervals of Difference (P1-P2)

Interval	Estimated	Confidence	Confidence
Method	Value	Limit	Limit
Chi-Square	0.2561	0.1456	0.3666

(Pearson)

(The calculation results are presented in the language of the original source)

In view of the considered nosology and absence of significant factors requiring a conservative approach for determination of the non-inferiority margin, for this purpose we can use a two-sided CI 90%. In such a case, the lower limit for the rate difference (a two-sided CI 95%) will amount to 14.6%. Therefore, a margin of 14.5% is considered to be justified.

Based on the above, we may hypothetically expect a rate of positive response to a new

	therapy (absence of a sore throat as an efficacy measure) at least 63%. A statistic hypothesis tested:		
	H0: $p_1-p_2 \le -14.5\%$ compared to H1: $p_1-p_2 > -14.5\%$ If a null hypothesis is rejected, a conclusion will be made that efficacy of the study drug is not less than that of the comparator drug.		
	A sample size is evaluated based on the following assumptions:		
	- A rate of positive response to therapy (absence of a sore throat as an efficacy measure) in a comparator drug arm is 63%.		
	- A rate of positive response to therapy (absence of a sore throat as an efficacy measure) in a study drug arm is 65% (chosen within the tested hypothesis and based on the sample size and expected positive response).		
	- Power = 80%		
	- A non-inferiority margin: 14.5		
	- Significance level: 97.5%		
	- Randomization in 1:1 ratio (study drug : comparator drug). A number of patients required at 80% power and 2.5% one-sided significance level to prove the hypothesis of the study drug efficacy not more than 14.5% inferior to that of the comparator drug (determined by absence of a sore throat after 3 days of therapy) if 128 patients in every arm.		
Interim analysis	An interim analysis may be conducted after receipt of efficacy data for Angal and ANTI-ANGIN ® FORMULA, spray, after 3 days of therapy, on Day 4, for 100 patients in every arm. The interim analysis includes demographic data, data on the anamnesis and concomitant therapy, available data on efficacy and safety of Angal and ANTI-ANGIN ® FORMULA drugs.		
Blinding, randomization	This trial will be open, without blinding. The patients will be included by randomization in 1:1 ratio using envelopes at the trial site.		

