### 9.1.2. Analysis of the primary efficacy endpoint

The primary outcome measure in this trial was the proportion of patients without sore throat after 3 days of therapy, on Day 4, as evaluated by the Investigator according to the Tonsillopharyngitis Severity Score (TSS), in both Angal and ANTI-ANGIN® FORMULA arms.

A null hypothesis of this trial assumes that Angal, the study drug, is less effective than ANTI-ANGIN® FORMULA, the comparator drug. An alternative hypothesis of this trial assumes that Angal, the study drug, is not less effective than ANTI-ANGIN® FORMULA, the comparator drug.

14.5% is chosen as a non-inferiority margin (see Section 9.2 for a justification) based on the results of a randomized, placebo-controlled trial of a similar drug.

The group comparison will be carried out using the Fisher's exact test (one-sided test, in connection with the null hypothesis of non-inferiority).

For the proportion difference, the 90% confidence interval (CI) will be calculated according to the procedure described in Newcombe, Robert G. "Interval Estimation for the Difference Between Independent Proportions: Comparison of Eleven Methods," Statistics in Medicine, 17, 873-890 (1998).

Thus, the non-inferiority will be confirmed if the limit of the two-sided 90% confidence interval for the difference in the proportions will be 14.5% or lower.

A primary endpoint analysis will be conducted both for the ITT (main analysis) and PP populations (additional analysis).

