#### **Confidence Intervals of Difference (P1-P2)**

Interval	Estimated	Confidence	Confidence
Method	Value	Limit	Limit
Chi-Square (Pearson)	0.2561	0.1456	0.3666

(The calculation results are presented in the language of the original source, i.e., from NCSS 8 statistical program).

- This is a non-inferiority trial; therefore, a non-inferiority margin for the primary endpoint should be justified and amount to not more than 14.5%.
- An expected rate of positive response to therapy (absence of a sore throat as an efficacy measure) in a comparator drug arm is 63%.
- An expected rate of positive response to therapy (absence of a sore throat as an efficacy measure) in a study drug arm is 65% (chosen within the tested hypothesis and based on the sample size and expected positive response).
- A one-sided type I error ( $\alpha$ ) = 2.5 % (0.025)
- A type II error ( $\beta$ ) = 20% (0.2), which corresponds to 80% power.
- Expected discontinuation from the trial will amount to 10% during the treatment.

The tested hypotheses are worded as follows:

1. Null hypothesis (Ho): Difference in the primary endpoint achievement incidence while using Angal, the study drug, and ANTI-ANGIN® FORMULA, the original drug, for treatment of acute infectious and

inflammatory pharyngeal diseases will exceed 14.5% in favor of ANTI-ANGIN  $^{\circledast}$  FORMULA:

$$H_0: p_1 - p_2 \le -0.145$$

2. Alternative hypothesis (HA): Difference in the primary endpoint achievement incidence while using Angal, the study drug, and ANTI-ANGIN® FORMULA, the original drug, for treatment of acute infectious and inflammatory pharyngeal diseases will not exceed 14.5% in favor of ANTI-ANGIN® FORMULA

$$H_A: p_1 - p_2 > -0.145$$

Where p1 and p2 is the primary endpoint achievement incidence while using Angal, the study drug, and ANTI-ANGIN® FORMULA, the original drug, respectively.

To calculate a sample size in every group, one can use a formula presented by Chow S, Shao J, Wang H. 2008. Sample Size Calculations in Clinical Research. 2nd Ed. Chapman & Hall/CRC Biostatistics Series. page 90:

$$n = (p_1 \times (1 - p_2) + p_2 \times (1 - p_2)) \times \left(\frac{z_{1-\alpha} + z_{1-\beta}}{p_1 - p_2 - \delta}\right)^2$$

where:

- n = Size of one group;
- z = Normal distribution function at the set levels of  $\alpha$  and  $\beta$ ;
- $\delta$  = Non-inferiority margin;
- p1 = Expected proportion in Angal group;

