#### 9.6 **Procedures for reporting any deviations from the original statistical plan**

All deviations from an initial statistical plan must be described and justified in a protocol amendment and/or a final trial report (in the last case, a statistical analysis plan developed before the start of a final statistical analysis must contain a list of those deviations with justification for the reasons thereof).

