# 1 Introduction

This trial has been designed and conducted to evaluate the therapeutic efficacy and safety of the study drug Angal, lozenges [menthol], 1.0 mg + 5.0 mg (Sandoz d.d., Slovenia), comparing to ANTI-ANGIN® FORMULA, lozenges, 0.2 mg + 2.0 mg + 50 mg (OOO Valeant, Russia), in the treatment of patients with uncomplicated acute infectious and inflammatory diseases of the pharynx accompanied by a sore throat. The objective of this Phase III trial is to demonstrate the non-inferior therapeutic efficacy of the study drug as compared to the reference product.

This Statistical Analysis Plan was developed in accordance with the following documents:

- Guidelines for examination of medicinal products, Vol. 1. Federal State Budgetary Institution Scientific Center for Expert Evaluation of Medicinal Products under the Ministry of Health of the Russian Federation (eds. A.N. Mironov). Moscow: Grif and K, 2013.
- ICH harmonised tripartite guideline. Statistical principles for clinical trials (E9). Current Step 4 version dated 5 February 1998.
- GCP rules of the Eurasian Economic Union (a draft).

The objective of this Statistical Analysis Plan is more detailed, compared to Section 9 of the trial protocol, description of the main principles of the protocol-based statistical analysis, description of the primary and secondary endpoints analysis methods, as well as other data obtained during the trial.

This Plan stipulates for consistence of the scheduled and conducted statistical analysis to the trial protocol, including definition of the analysis data sets, transformations and calculations for the endpoints, observations quantity needed, etc. No changes in this Statistical Analysis Plan compared to the trial protocol are envisaged.

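### The trial is sized and thresholded at one-sided 2.5%, but non-inferiority is decided on a two-sided 90% CI (one-sided 5%), and SAP 3.10 moves the p threshold to 0.05 without declaring it

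*SAP*

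**What the plan says.** **Sizing.** The protocol synopsis gives the sample size as "A number of patients required at 80% power and 2.5% one-sided significance level to prove the hypothesis". Protocol 9.2 repeats it: "A one-sided type I error" is set to 0.025 with 80% power. The software table in the same section shows a one-sided confidence level of 0.975.

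**Threshold in the protocol.** For the primary endpoint, Protocol 9.3 states that "an one-sided statistical criterion will be used with 97.5% significance level (a threshold p value is below 0.025".

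**Decision rule in the protocol.** The next paragraph of 9.3 says that "90% CI will be calculated for the proportions difference with further evaluation of its lower boundary limit". Protocol 9.1.2 makes that interval the criterion: "non-inferiority will be confirmed if the limit of the two-sided 90% confidence interval for the difference in the proportions will be 14.5% or lower".

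**SAP.** Sections 3.10, 4 and 4.1.2 keep the two-sided 90% interval. Section 3.10 replaces the protocol threshold: "a one-sided statistical criterion will be used with 95% significance level (a threshold p value is below 0.05".

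**Change control.** SAP section 1 says "No changes in this Statistical Analysis Plan compared to the trial protocol are envisaged". Protocol 9.6 requires that "All deviations from an initial statistical plan must be described and justified in a protocol amendment and/or a final trial report". If the report is the place chosen, 9.6 adds that the SAP must list the deviations with reasons. The SAP has no such list.

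**The concern.** Declaring non-inferiority when the lower limit of a two-sided 90% interval clears the margin is a one-sided 5% test. Protocol 9.2 makes the same equivalence when it describes its 90% lower limit as a one-sided 95% limit. Protocol 9.3 therefore holds two error rates for one hypothesis, and the SAP settles the conflict at the looser level without saying so.

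Two things are at stake. The rule to be applied does not hold the 2.5% error that the protocol states. A result whose 90% limit clears -14.5 points but whose 95% limit does not meets the interval rule in both documents, yet misses the 2.5% level in Protocol 9.3. The same data would support opposite conclusions, and choosing the level after seeing them would be data-dependent. SAP section 4 rests the efficacy conclusion on this endpoint alone.

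**Working it through.** **Inputs.** Protocol synopsis and 9.2: comparator rate 63%, Angal rate 65%, margin 14.5 points, 1:1 allocation, 80% power, one-sided alpha 0.025, 128 evaluable per arm, 140 randomised per arm, 10% loss. Protocol 9.1.2 and SAP 4.1.2: Newcombe interval. The article cited compares several methods and the plan does not say which is meant. I assume the hybrid Wilson score interval without continuity correction.

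**1. Which alpha does 128 per arm belong to?** Standard unpooled formula:

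n = [p1(1-p1) + p2(1-p2)] × [(z(1-α) + z(1-β)) / (p1 - p2 + 0.145)]²

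- Variance term: 0.65×0.35 + 0.63×0.37 = 0.4606. Denominator: 0.02 + 0.145 = 0.165.
- α = 0.025: 0.4606 × [(1.960 + 0.8416)/0.165]² = 132.8, so 133 per arm.
- α = 0.05: 0.4606 × [(1.645 + 0.8416)/0.165]² = 104.6, so 105 per arm.

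The stated 128 is not reproduced exactly. The formula as printed in 9.2, with (1-p2) in both terms, gives 137. The software run behind 128 used 1000 simulations. Power at 128 and α = 0.025 is 78.5% by normal approximation, close to the stated 80%. So 128 is near a 2.5% design and well above what a 5% design needs.

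**2. Error and power of each rule.** Lower limit of the interval:

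L = d - √[(p̂1 - l1)² + (u2 - p̂2)²]

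Here d = p̂1 - p̂2, l1 is the Wilson lower limit for Angal and u2 the Wilson upper limit for the comparator. Non-inferiority is declared if L > -0.145. Binomial probabilities are summed over all outcomes with 128 per arm:

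| True rates (Angal v comparator) | 90% CI rule | 95% CI rule |
|---|---|---|
| 48.5% v 63% (at the margin: type I error) | 4.91% | 2.81% |
| 65% v 63% (planning assumption: power) | 87.38% | 79.16% |
| 63% v 63% (power) | 78.55% | 67.95% |

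- Ratio of errors: 4.91 / 2.81 = 1.75.
- Every trial that passes the 95% rule also passes the 90% rule, so the difference is the chance of a split result: 87.38 - 79.16 = 8.2% at the planning rates, and 78.55 - 67.95 = 10.6% if both rates are 63%.

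**3. A split result.** Take 81/128 (63.3%) on the comparator. Angal needs at least 76/128 under the 90% rule and 78/128 under the 95% rule. At 77/128 (60.2%), d = -0.0313:

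- 90%: l1 = 0.5290, u2 = 0.6995. L = -0.0313 - √(0.0726² + 0.0667²) = -0.130.
- 95%: l1 = 0.5150, u2 = 0.7113. L = -0.0313 - √(0.0866² + 0.0785²) = -0.148.

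The first clears -0.145 and the second does not. A margin-shifted score test (Farrington-Manning) gives one-sided p = 0.029, between 0.025 and 0.05. That test is used here for illustration; neither document plans it.

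**4. The planned p value.** The only test named for the primary endpoint is a one-sided Fisher's exact test, with no margin shift. At 83/128 v 81/128, close to the expected rates, its p value is 0.448. A threshold applied to it does not test H0: p1 - p2 ≤ -0.145.

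**The case against.** The strongest reply is that the operative rule never changed. The only sentence saying when non-inferiority is confirmed is the 90% interval rule, and it is the same in Protocol 9.1.2 and SAP 4.1.2. On that view SAP 3.10 only brought the p threshold into line. It is true that the root is inside the protocol. But nothing there says the interval overrides p<0.025, and the sizing supports 2.5%. The protocol's one rationale for a 90% interval concerns deriving the margin from the earlier placebo-controlled trial, not this trial's test.

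Other points that stand in part:

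- **The p = 0.029 example uses an unplanned test.** Correct. Under the planned Fisher test, 77/128 v 81/128 gives one-sided p of 0.74 or 0.35, depending on direction, and misses both thresholds. The split in step 3 rests on the two interval limits and does not need a p value.
- **A 95% Newcombe rule also exceeds 2.5%.** Correct: 2.81% at 128 per arm, 2.95% at 126 and 2.77% at 140. The excess is small beside 4.9%.
- **The looser rule does not harm power.** Correct: it raises power. The problem is the error rate and the contradiction.
- **5% could be a legitimate choice.** Yes, if it is declared and justified beforehand, which has not been done.
- **These figures ignore the interim look.** Correct. SAP 3.7 allows an efficacy look without adjusting the level. That is a separate matter, but the trial-wide error may be higher than shown.

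**Conclusion.** The point holds and must be fixed before analysis. The documents state one-sided 2.5% for sizing and for the protocol threshold, one-sided 5% through the interval rule in both documents, and p<0.05 in the SAP with no declared change. The nominal one-sided error of the decision rule is twice the stated level. The exact error is about 1.75 times that of a 95% rule (4.9% v 2.8%), and the two rules disagree in about 8% of trials under the planning assumptions. These figures assume a hybrid Wilson score interval without continuity correction, 128 evaluable per arm, a comparator rate of 63% and no interim look. The contradiction between the stated levels depends on none of these assumptions.

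**What to change.** Use one alpha in every place. To match the sizing:

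- Restore p<0.025 for the primary endpoint in SAP 3.10.
- Replace the 90% interval by a two-sided 95% interval in Protocol 9.1.2 and 9.3, in SAP 3.10, 4 and 4.1.2, and in SAP Figure 2.
- State the rule with its sign: non-inferiority is concluded if the lower limit of the two-sided 95% CI for p1 - p2 (Angal minus ANTI-ANGIN) lies above -14.5 percentage points.
- Name the interval as the sole decision rule. Any p value held to 0.025 should come from a test of H0: p1 - p2 ≤ -0.145, not from the unshifted Fisher test.
- In the synopsis, relabel the 14.6% limit as coming from a two-sided 90% interval, as Protocol 9.2 already does.

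If the sponsor intends one-sided 5%, it should declare and justify this under Protocol 9.6 before analysis, and restate alpha and power in the synopsis, 9.2 and 9.3.

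The cost is wording in both documents, with 280 randomised unchanged. The price of the 95% rule is power. At 65% v 63% it is 78.9% with 126 evaluable per arm (140 × 0.9), 79.2% with 128 and 82.7% if all 140 are evaluable. At the planned loss it is therefore about one point under the stated 80%, and the plan should say so.
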